Standard initial treatment for glioblastoma currently consists of surgical removal of as much of the MRI contrast-enhancing lesion as can be accomplished safely, followed by radiotherapy and temozolomide (TMZ) chemotherapy for 6 weeks. Unfortunately, early treatment failures occur in 30-50% of patients. This definition of treatment failure is described as an increase in the MRI T1+Gd tumor volume (de Wit, 2004). Immediate post-radiotherapy MRI changes in malignant glioma can mimic tumor progression (Taal, 2008). The incidence of this pseudo-progression in a cohort of malignant glioma patients treated with chemo-radiation with temozolomide is significant (Brandes, 2008). From 28-52% of these patients will demonstrate improvement on subsequent MRI studies when they continue on standard TMZ chemotherapy. This situation defines pseudo-progression as opposed to true disease progression, where continued treatment with temozolomide is associated with continued clinical decline and MRI T1+Gd worsening. Clinicians armed with anatomic MRI imaging alone may wrongly conclude that standard treatment is failing in these patients, leading to cessation of a treatment that is actually working. Also, misdiagnosing pseudo-progression in patients who are responding could risk entering such patients into phase II or III trials of new agents, decreasing the statistical power of the study and potentially leading to falsely positive outcomes. On the other hand, continuing TMZ in the patients that are true progressors wastes their time and physiological resources when they should be offered second line treatment or enrollment in a phase II or III research treatment protocol. Thus, the ability to make the important distinction between progression and pseudo-progression is critical for the care of treated brain tumor patients and could potentially change patient management. In some patients, the neuropathologist who reviews the resected tumor resolves the question of pseudo-progression versus true progression. Ideally, however, noninvasive imaging methods should be developed to answer this question reliably. Our primary hypothesis is that FLT PET/CT should be able to distinguish between when the patient has true tumor progression and needs to change therapy and when the MRI contrast is reflecting pseudo-progression and the patient should continue with TMZ chemotherapy. That way, the 50% or possibly more true progressors could avoid continuing futile TMZ.

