Figure 6.iii.3 Kinetic model of FLT metabolism is comprised of an exchangeable tissue compartment and a compartment of trapped FLT \ nucleotides. Four rate constants describe kinetic transfer rates between the 2 compartments. FLTMP = FLT-monophosphate; FLTDP = FLT-diphosphate; FLTTP = FLT-triphosphate; FLT-gluc = FLT-glucuronide; Q_e = exchangeable tissue compartment; Q_m = compartment of trapped FLT phosphorylated nucleotides; $C_{p\text{FLT}}$ = concentration of FLT in arterial plasma; C_{met} = concentration of metabolites in arterial plasma. An imaged extraction procedure will be used to recover the arterial input function (O'Sullivan, et al. 2010).

6.iii.10.a.1. Compartmental Analysis

From PET/CT VOI analysis of dynamic data, SUV (30-60 min summed) and parameters reflecting transport (K_1) and FLT flux (K_{FLT}) will be calculated using mathematical modeling analysis as described by Muzi et al (Muzi, 2005a; Muzi, 2005b). The change in these rate parameters between baseline and follow up imaging will also be calculated.

6.iii.10.b. Biologic Correlates

Blood Collection Time Points

Blood samples will be obtained from each participant at the time of dynamic PET imaging. Each blood sample is used both for the determination of radioactivity and metabolite analysis. Blood samples are drawn from patients using a second venous catheter placed in the opposite arm from the injection site or from a clinically placed PICC line or Port-a-cath. Blood samples of 2-3 mL each are collected into heparinized syringes (or a heparinized blood vacutainer) at 15, 30 and 60 minutes after ¹⁸F-FLT injection, which is infused over one minute.

No tissue sampling other than what is required for clinical diagnosis will be done for this study. At the time of resection (or re-resection), tissue not needed for standard clinical care may be labeled with anatomic location co-registered to the PET images and banked for potential future analysis of biomarkers. Any biomarker studies would be described in a separate IRB protocol and would be consented separately from the FLT PET/CT imaging protocol. This consent is already part of the consent for surgery.

6.iii.11. STUDY CALENDAR

Table 6.iii.4

	Pre-Study	Day of [¹⁸ F]FLT baseline	Mid-Rx	Post-therapy Day of [¹⁸ F]FLT (optional)	Post-Rx 1 year or time of suspected recurrence [¹⁸ F]FLT
Confirmed diagnosis of malignant brain tumor	X				
Informed Consent	X				
Demographics	X				
Pregnancy Test **		X		X	X
Vital Signs *	X				

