The analysis of data for these hypotheses involves within-subject changes where the variance in values will be less than between-subject FLT results that we have published. Furthermore, this power analysis has assumed that only data from a single volume of interest (VOI) for each subject will be used. In the context of our aims, this could be considered inefficient. In many subjects it will be possible to include data from spatially well-separated and hence substantially uncorrelated sub-regions within large tumors (Spence, 1998) as distinct sampling units for consideration with this hypothesis. Notwithstanding the additional variability that sub-region measurements will have, it is likely that some gains in statistical precision can be realized by this approach. Thus the 90% power estimate is conservative.

Hypothesis 1. Among GBM patients identified as progressing according to Macdonald criteria at 1-month follow-up, the mean FLT flux in true progression cases will be compared to the corresponding mean in the pseudo-progression cases. Preliminary data indicate that 40% of MRI diagnosed progression can be expected to be pseudo-progression. Our data on recurrence vs radionecrosis for KFLT recurrences showed a mean of 0.017 and a standard deviation of 0.005 (Spence, 2006). The mean of the radionecrosis group was 0.004, roughly one-quarter for that for recurrences. Thus, conservatively, assuming that pseudo-progressors showed even a 30% increase over the mean KFLT value, the expected difference between the groups would be 0.017×0.3 or about 0.005. From this, the expected standardized effect is 0.99. Using a 2-sample t-test with significance level of 5% for assessment of the hypothesis, the power of our study is about 95%.

6.iii.14.c. Analysis Plan

Percentage change between pre-treatment and post-therapy measurements will be computed for [¹⁸F]FLT PET/CT measures of transport, K₁, and flux (KFLT). Log transformations will be considered if the rates of change are highly skewed. Outcome analysis studies are directed toward predicting tumor response. In the case of progression, a multivariate logistic regression will be used to produce an analysis of how the combination of standard diagnostics plus the FLT parameters (K₁, KFLT, SUVmean) obtained shortly after therapy can best be combined to

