obtain a prognostic variable for determination of progression. Although the prognostic variable will provide a direct assessment of the probability of response for an individual patient, we will also develop a ROC characterization of its diagnostic performance. We fully appreciate that the small number of patients means that this analysis may suffer from a lack of power but it should be useful in planning a larger follow-up if the results are encouraging.

A similar approach will be used for survival analysis.. Here we will use multivariate Cox regression analysis with both baseline and follow-up variables to be considered.

The heterogeneity of the within-tumor proliferation obtained by application of the elliptical heterogeneity measure developed by Eary et al (2008) will be used in a secondary analysis.

6.iii.14.d. Stratification Factors

Not Applicable.

6.iii.14.e. Reporting and Exclusions

Evaluation of Toxicity: All patients will be evaluable for toxicity from their [¹⁸F]FLT PET.

6.iii.15. LITERATURE CITED

Carlson RW. Sequencing of endocrine therapies in breast cancer--integration of recent data. *Breast Cancer Res Treat* 2002; 75 Suppl 1 S27-32; discussion S33-5.

Carlson RW, Allred DC, Anderson BO, Burstein HJ, Carter WB, Edge SB, Erban JK, Farrar WB, Goldstein LJ, Gradishar WJ, Hayes DF, Hudis CA, Jahanzeb M, Kiel K,

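### The progression model in 6.iii.14.c is an unpenalised logistic regression that can fail to yield finite estimates if the FLT contrast is as large as the preliminary data; Firth estimation would prevent this at little cost

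*Combined protocol and SAP*

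**What the plan says.** Section 6.iii.14.c (Analysis Plan) states: "In the case of progression, a multivariate logistic regression will be used". Its predictors are "the combination of standard diagnostics plus the FLT parameters (K₁, KFLT, SUVmean) obtained shortly after therapy". The diagnostics are not listed or counted. No penalty, predictor limit, test of the FLT terms or rule for a non-converging fit is given. The section goes on to promise that "the prognostic variable will provide a direct assessment of the probability of response for an individual patient", and adds an ROC analysis. It concedes that small numbers may mean low power, and presents the analysis as useful for planning a larger study.

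Section 6.iii.10.a.1 shows that the three FLT measures share one source: "From PET/CT VOI analysis of dynamic data, SUV (30-60 min summed) and parameters reflecting transport" (K1), together with FLT flux.

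Section 6.iii.14.b gives two sizes of FLT contrast. For KFLT, recurrences "showed a mean of 0.017 and a standard deviation of 0.005". Then: "The mean of the radionecrosis group was 0.004, roughly one-quarter for that for recurrences". For power, the plan takes a smaller difference, which it calls conservative, and states that "the expected standardized effect is 0.99". Hypothesis 1 is tested separately, by a two-sample t-test on mean flux.

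**The concern.** A logistic regression has no finite maximum-likelihood solution when some linear combination of the predictors splits the two outcome groups perfectly. This becomes more likely with fewer patients, more predictors and a stronger true effect. The plan has few patients and at least four predictors, since the diagnostics are plural in the text but uncounted. Its preliminary data also suggest that the effect could be strong. So the better FLT discriminates, the more often the planned fit would break down.

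At stake is the output that the section promises. Under complete separation every fitted probability goes to 0 or 1, and the in-sample ROC curve looks perfect whatever the true performance. Neither would be a sound basis for designing the larger study. The plan's caveat about power does not cover this, because the problem is not low power.

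**Working it through.** **Effect sizes.** The plan's planning difference is 0.017 × 0.3 = 0.0051. Divided by 0.005 this is 1.02, or 1.0 with the rounded difference, close to the stated 0.99. The preliminary contrast is (0.017 − 0.004)/0.005 = 2.6 SD. The radionecrosis SD is not given, so 2.6 assumes a common SD of 0.005.

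**The plan's own figure.** No power is stated for the logistic model. The stated power of about 95% belongs to the Hypothesis 1 t-test. At 0.99 SD, two-sided 5% and a 60:40 split it recomputes to 73% with 18:12 patients and 85% with 24:16. That is a separate matter and is not used below.

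**Patients.** The documents give 30 planned and up to 40 enrolled (6.iii.14.a, 6.iii.4.d). If the model covers only early progressors, section 6.iii.3.a says that "early treatment failures occur in 30-50% of patients" with glioblastoma: 0.30 × 40 = 12 to 0.50 × 40 = 20, even if all 40 had glioblastoma. The 60:40 split comes from the 40% pseudo-progression rate in 6.iii.14.b.

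**Model and check.** logit P = β0 + β1·K1 + β2·KFLT + β3·SUVmean + γ′D, where D holds the diagnostics. The data separate if some vector b gives x′b ≥ 0 for every patient in one group and x′b ≤ 0 for every patient in the other, not all of them zero. Multiplying b by an ever larger factor then keeps raising the likelihood, so no finite maximum exists. Separation was checked by linear programming in 200 to 500 simulated datasets per setting.

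**Assumptions not in the documents.** Correlation among the FLT terms is 0.5 to 0.8. KFLT is shifted by d. K1 and SUV are shifted either by 0.5d and 0.8d, or both by the correlation times d.

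**Separation rates.** The 2.6 SD column uses two diagnostics; the 0.99 SD column is the range over the settings run.

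| Patients | 2.6 SD | 0.99 SD |
|---|---|---|
| 40 (24:16) | 37-60% | about 0% |
| 30 (18:12) | 56-79% | 1-5% |
| 20 (12:8) | 85-94% | 12-27% |
| 15 (9:6) | 94-98% | 39-61% |

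**Sensitivity at 2.6 SD** (K1 and SUV shifted by the correlation times d). At 18:12 the rate is 37-38% with no diagnostics, 47% with one, 56-64% with two, 74-75% with three and 83% with four. At 24:16 it is 18-23% with none, 37-42% with two, 50-52% with three and 63% with four. If the radionecrosis SD were 0.002, it would be 86-96% at 18:12.

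**Which tests fail** (18:12, 2.6 SD, two or three diagnostics, unpenalised fit). The Wald test for KFLT is significant in 1-12% of datasets, and in none of the separated ones. The 1-df likelihood-ratio test for KFLT rejects in 47-93%. The joint 3-df likelihood-ratio test of the FLT terms and the t-test each reject in about 100%.

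**Changing only the penalty.** Firth's method maximises log L(β) + ½ log|I(β)|, which keeps estimates finite. With identical predictors it lowered out-of-sample log-loss in all 16 settings run. At n=30 with two diagnostics, log-loss fell from 1.26 to 0.29 at 2.6 SD and from 0.84 to 0.62 at 0.99 SD. For scale, giving every patient a probability of 0.6 scores −(0.6 ln 0.6 + 0.4 ln 0.4) = 0.67, taking natural logs and the same 60:40 split. The unpenalised figures depend partly on where a diverging fit is stopped; the direction does not.

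**Power of the penalised tests** (two diagnostics, correlation 0.8):

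| Setting | Joint FLT test | KFLT adjusted for K1, SUV | KFLT as only FLT term |
|---|---|---|---|
| 2.6 SD, 18:12 | about 100% | 35% | about 100% |
| 2.6 SD, 12:8 | 96% | 11% | 100% |
| 2.6 SD, 9:6 | 58% | 3% | 95% |
| 0.99 SD, 18:12 | 43% | 24% | 62% |
| No effect, 18:12 | 3% | 3% | 6% |

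**The case against.** A reader might infer that the planned analysis would miss a strong FLT effect. The documents do not support that. They name no Wald test, and the stated aim is to combine the parameters into a prognostic variable. The joint likelihood-ratio test still finds a 2.6 SD effect, and Hypothesis 1 has its own t-test. This part of the defence stands.

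It is also fair that 2.6 SD is not the plan's assumed effect. It comes from recurrence versus radionecrosis, not true versus pseudo-progression, and needs an assumed common SD. At 0.99 SD with 30 to 40 patients, separation is rare. The number of diagnostics is unknown too: with none or one, separation at n=30 stays below half under a common SD. Nor is it settled that the model is limited to progressors. The wording could mean progression as an outcome among all patients, in which case neither the 60:40 split nor the 2.6 SD contrast carries over directly.

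Another tempting step is to cut the model to KFLT alone. The gain in power for KFLT comes mainly from dropping K1 and SUV, not from the penalty, and the plan explicitly sets out to learn how the three combine. That is a trade-off, not a correction. Extending the point to the Cox model was not examined and is not claimed.

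Lastly, this is a pilot with a stated caveat, and separation would be visible at analysis. But seeing it then leaves the method to be chosen after the data are known, and the promised probabilities would still lack a specified way to obtain them.

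**Conclusion.** The concern holds in a conditional form. As written, 6.iii.14.c has no safeguard against separation. If the contrast approaches 2.6 SD and two diagnostics are used, the planned fit has no finite solution in roughly 55-80% of datasets at n=30, about 40-60% at n=40 and about 90% at n=20. At 0.99 SD the risk is about 0-5% at n=30-40, and becomes material only in a small subset: 12-27% at n=20 and 39-61% at n=15. These rates rest on the assumed correlations, shifts, common SD and number of diagnostics.

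The damage is to the coefficients, the individual probabilities and the apparent ROC curve. Detection of an FLT effect is lost only if single-coefficient Wald tests are relied on. The change is worth making because it is nearly free and improves the predictions even at the planning effect.

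**What to change.** In 6.iii.14.c, fit the progression model by Firth penalised logistic regression. Report profile penalised-likelihood intervals and a joint penalised likelihood-ratio test of K1, KFLT and SUVmean, and take the individual probabilities from that fit. Name the standard diagnostics in advance and limit them to one or two. State whether the model covers all patients or only those with apparent progression. A model with KFLT as the only FLT term may be added as a sensitivity analysis, but need not replace the three-parameter combination.

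The cost is a few lines of text, a standard software option, slight shrinkage of the coefficients and a small amount of extra analysis work. The penalty does not cure small numbers: at 0.99 SD and 18:12 the joint test has about 43% power in the setting above, so the plan's caveat about power should stay.

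### The ROC of the fitted progression score has no internal validation, so its AUC would be biased upward, by about 0.05 to 0.23 at n = 30 depending on assumptions the plan does not fix

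*Combined protocol and SAP*

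**What the plan says.** The Analysis Plan (6.iii.14.c) sets out the outcome model as "a multivariate logistic regression will be used to produce an analysis of how the combination of standard diagnostics plus the FLT parameters" K1, KFLT and SUVmean, measured shortly after therapy, can be put together to best effect as a prognostic variable for progression. For that variable, "we will also develop a ROC characterization of its diagnostic performance". The section concedes that with few patients "this analysis may suffer from a lack of power but it should be useful in planning a larger follow-up if the results are encouraging".

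The population is introduced only by the words "In the case of progression, a multivariate logistic regression will be used". The standard diagnostics are not listed. Survival is to be handled in a similar way: "Here we will use multivariate Cox regression analysis with both baseline and follow-up variables to be considered".

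The Statistical Considerations plan for 30 patients. Accrual Targets (6.iii.4.d) allows up to 40, because 25% are expected to have only one or two scans (40 × 0.75 = 30). Nowhere do the documents mention cross-validation, bootstrap correction, shrinkage, a hold-out set or a score fixed in advance.

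**The concern.** A logistic fit chooses the weights that best separate the patients it is given. If the ROC of that score is drawn in those same patients, part of the separation is noise that will not recur. The AUC is then optimistic, and more so when there are few events per predictor, as here.

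The stated caveat addresses a different risk. Low power means that a real effect may be missed. Optimism means that a weak or useless score may look good. A reader who knows only about low power would find a high AUC from a small study more convincing, when the small sample is part of the reason it is high.

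What is at stake is the use the plan gives this analysis, which is to inform a larger follow-up study if the results look encouraging.

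**Working it through.** The plan states no AUC and no sample-size figure for this model, so there is no figure to reproduce. The size of the bias was estimated by simulation.

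**Inputs from the documents**
- n = 30, with 40 as the ceiling.
- Three FLT parameters: K1, KFLT and SUVmean.
- The KFLT planning effect in 6.iii.14.b: "the expected standardized effect is 0.99".
- The raw KFLT contrast in the same section, recurrence against radionecrosis: (0.017 − 0.004)/0.005 = 2.6 SD.

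**Inputs assumed, because the documents do not give them**
- 12 events in 30.
- Two standard diagnostics, so five predictors in all, one of the diagnostics shifted 0.7 SD between outcome groups.
- Independent normal predictors.

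**Method.** For each simulated dataset (4,000 per cell; 1,500 for the 2.6 SD cell) an essentially unpenalised logistic model was fitted.
- Apparent AUC = [R₁ − n₁(n₁ + 1)/2]/(n₁n₀), where R₁ is the rank sum of the fitted score among the n₁ events and n₀ is the number of non-events.
- New-patient AUC of the same fitted score = Φ(w′d/√(2w′w)), where w is the fitted weights and d the true mean shifts.
- Best attainable AUC = Φ(√(d′d)/√2). With only the 0.7 SD diagnostic this is Φ(0.7/1.414) = 0.69.

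**Results, n = 30 with 12 events**

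| What is informative | Apparent | New patients | Gap |
|---|---|---|---|
| One diagnostic 0.7 SD, KFLT 2.6 SD | 0.99 | 0.94 | 0.05 |
| One diagnostic 0.7 SD, KFLT 0.99 SD | 0.87 | 0.74 | 0.12 |
| One diagnostic 0.7 SD, FLT uninformative | 0.79 | 0.62 | 0.17 |
| Nothing | 0.73 | 0.50 | 0.23 |

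Gaps are taken before rounding. In the last row about 65% of datasets give an apparent AUC of 0.70 or more.

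**Sensitivity, uninformative-FLT case.** Apparent/new-patient AUC is 0.81/0.61 with 8 events in 30, 0.79/0.62 with 15 or 18 events, 0.79/0.62 with the FLT parameters correlated 0.8, and 0.77/0.63 with 16 events in 40. The apparent AUC was the higher one in every cell.

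**If only MRI progressors enter.** Section 6.iii.3.a says of glioblastoma that "early treatment failures occur in 30-50% of patients". That gives at most 0.30 × 30 = 9 to 0.50 × 30 = 15 patients (12 to 20 of 40), even if every enrolled patient had glioblastoma. Section 6.iii.14.b adds: "Preliminary data indicate that 40% of MRI diagnosed progression can be expected to be pseudo-progression". With 15 progressors, 0.60 × 15 = 9 are true progressions. With uninformative FLT the result is then 0.89/0.58, a gap of about 0.31. With nothing informative it is 0.85/0.50, and 18% of datasets show complete separation.

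**Does a correction work?** A bootstrap optimism correction was applied with 200 resamples per dataset and 250 to 400 datasets per cell:

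| Case | Apparent | Corrected | New patients |
|---|---|---|---|
| n = 30, FLT uninformative | 0.79 | 0.66 | 0.62 |
| n = 30, KFLT 0.99 SD | 0.87 | 0.77 | 0.74 |
| n = 30, nothing informative | 0.73 | 0.58 | 0.50 |
| n = 15, FLT uninformative | 0.88 | 0.70 | 0.58 |

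At n = 30 it removes most of the bias. At n = 15 a difference of about 0.12 remains.

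**The case against.** The strongest reply is that this is a pilot. The documents describe the data as preliminary, the aim as exploring associations, and the sample as small. The ROC supplements the model, no decision threshold rests on it, and harm requires a later planner to take a 30-patient ROC at face value. All of that stands, and it limits the consequence. It does not remove the bias, because informing the next study is the use the plan names for this analysis.

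A second reply is that the plan is silent rather than committed: it names no estimator and does not exclude resampling. That is fair. The claim is only that the plan, carried out as written, yields the apparent AUC.

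Third, a reader might take the 0.79 versus 0.62 case as the expected bias. The documents do not support that. It makes all three FLT parameters useless, whereas the protocol plans on 0.99 SD for KFLT and cites data with a raw contrast of 2.6 SD. The 0.99 SD is itself borrowed: it concerns true versus pseudo-progression among glioblastoma progressors, while the trial admits any primary, recurrent or metastatic brain tumour. Only the direction of the bias is firm, and its size is a range.

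Fourth, a reader might extend the criticism to the Cox analysis. The plan names no performance measure for that model, so no biased figure can be attributed to it.

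**Conclusion.** The point holds, as a matter that should be corrected. The plan optimises a score and describes its ROC in the same patients without validation, and its caveat addresses a different problem. Assuming 12 events in 30 and five predictors, the AUC would be too high by about 0.05 to 0.23. The gap is about 0.12 at the protocol's own KFLT effect, and about 0.3 if only 15 MRI progressors enter and FLT is uninformative. The event count, the number and strength of the diagnostics, and the analysis set are assumptions.

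The consequence is limited to planning the follow-up study. A reader might infer that the test of Hypothesis 1 or patient care is compromised. Neither is: Hypothesis 1 uses a two-sample t-test that does not involve this score, and the protocol states that FLT results do not direct treatment.

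**What to change.** In 6.iii.14.c:

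1. State which patients enter the logistic model (all patients or MRI progressors only) and list the standard diagnostics.
2. Prespecify a bootstrap optimism correction that repeats the whole fitting procedure, including any variable selection, in each resample.
3. Make the corrected AUC the headline figure, and note that it stays mildly optimistic at this sample size (about 0.66 against 0.62 in the uninformative-FLT case).
4. If only MRI progressors enter, label the AUC descriptive.
5. If a performance measure is reported for the Cox model, correct it in the same way.

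A comparison with standard diagnostics alone is optional and should not be used as evidence that FLT adds value. In the uninformative-FLT case at n = 30, the three FLT terms raise the apparent AUC from 0.72 to 0.79 while lowering the new-patient AUC from about 0.66 to 0.62. Even after correction the difference averages 0.00 against −0.04 in new patients, exceeds 0.05 in 23% of datasets, and has a bootstrap 95% interval that covers the new-patient difference in only 76%.

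The cost is a few lines of wording and code, with no new data. The reported AUC will be less favourable and still imprecise.
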